## 4.6. Benefit: Risk Assessment

### **Pembrolizumab**

Specific information regarding warnings, precautions, contraindications, adverse events, and other pertinent information on pembrolizumab that may impact subject eligibility is provided in the pembrolizumab approved labelling. For detailed background information on pembrolizumab refer to [[Keytruda SmPC, 2017](#) and [KEYTRUDA PI, 2018](#), [Keytruda IB, 2021](#)].

### **Belantamab Mafodotin**

Summaries of non-clinical findings and information regarding warnings, precautions, contraindications, adverse events, and other pertinent information on belantamab mafodotin that may impact subject eligibility is provided in the Investigator's Brochure [[GlaxoSmithKline Document Number 2013N175128-09, 2021](#)]

#### 4.6.1. Risk Assessment

The risk assessment and risk mitigation plan for belantamab mafodotin and study procedures are summarized in [Table 2](#). Refer to [Table 5](#) for pembrolizumab guidance.

There is a risk of overlapping toxicities with the combination of belantamab mafodotin and pembrolizumab. Potential overlapping toxicities and risk mitigation plans are provided in [Table 2](#). The frequency and intensity of these assessments will allow Investigators and GSK to identify and to react to potential worsening of toxicities.

**Table 2 Risk Assessment and Mitigation Strategy**

Potential Risk of Clinical Significance	Summary of Data/Rationale for Risk	Mitigation Strategy
Potential overlapping toxicities for belantamab mafodotin in combination with pembrolizumab)		
Keratopathy (changes to the corneal epithelium, potentially resulting in vision changes)	
Belantamab mafodotin: Changes in corneal epithelium on ocular examination have been frequently observed with belantamab mafodotin. This was most commonly associated with: blurred vision, dry eyes, photophobia, and changes in visual acuity.
 
Participants with a history of dry eye were more prone to develop changes in the corneal epithelium.
	
Active monitoring for corneal events according to Table 4.
 
Timely evaluation and management by an ophthalmologist (or an optometrist if an ophthalmologist is not available) upon developing corneal related events (see Section 6.5.1 and Appendix 9).

Eye disorders associated with pembrolizumab	
Based on available follow-up data, visual acuity returned to, or near baseline in most cases and no permanent loss of vision reported.
 
Pembrolizumab: Eye disorders including dry eye, uveitis, and rarely Vogt-Koyanagi-Harada syndrome, have been reported with pembrolizumab.
	
In the event of new-onset eye-related symptoms (such as pain, significant loss of visual acuity, or bothersome foreign body sensation), participants are to urgently seek medical attention by a qualified eye care specialist (appropriate testing includes slit lamp examination [includes fluorescein staining] and measurement of visual acuity). Appropriate management should be initiated immediately as defined in Section 6.5.1.
 
Recommendations for dose delays / reductions are provided in Section 6.5.1.

Infusion related reaction	
Belantamab mafodotin: IRRs were reported in patients treated with belantamab mafodotin. Most IRRs observed to date were Grade 1 to 2 and manageable with medical treatment.
 
Pembrolizumab: Pembrolizumab may cause severe or life threatening infusion-reactions including severe hypersensitivity or anaphylaxis. Signs and symptoms usually develop during or shortly after drug
	
Subjects will be closely monitored for signs of IRR. Premedication prior to first infusion of belantamab mafodotin is not mandatory but may be considered based on investigator judgement.
 
If an IRR occurs during belantamab mafodotin administration, management may follow guidance in Table 4

Potential Risk of Clinical Significance	Summary of Data/Rationale for Risk	Mitigation Strategy
	infusion and generally resolve completely within 24 hours of completion of infusion.	or local standard of care. Management of pembrolizumab infusion reactions is provided in Table 6 .
Thrombocytopenia	
Belantamab mafodotin: Thrombocytopenic events of all grades (1-4) are among the most common AEs associated with belantamab mafodotin.
 
Pembrolizumab: Thrombocytopenia has been reported with pembrolizumab therapy.
	Hematological panels are assessed frequently. Supportive therapy (including transfusions) is provided according to standard medical practice, and dose reductions or treatment discontinuations are outlined in Section 6.5.
Neutropenia	
Belantamab mafodotin: Neutropenic events, including febrile neutropenia have been observed with treatment with belantamab mafodotin,
 
In a study of belantamab mafodotin in combination with lenalidomide/dexamethasone, two fatal cases of severe infections associated with neutropenia have been observed.
 
Pembrolizumab: Neutropenia has been reported with pembrolizumab therapy.
	
Hematological panels are assessed frequently.
 
Consider prophylactic antibiotics, per physician discretion and local institutional guidance, in subjects with Grade 3-4 neutropenia CCI even if afebrile.
 
Immediately hospitalize subjects with febrile neutropenia and initiation appropriate management, per local institutional guidance.
 
Consider additional supportive treatment(s) per local practice (e.g., growth factors).
 
Dose reductions or treatment discontinuations are outlined in Section 6.5

Potential for cardiotoxicity related to an inflammatory	Belantamab mafodotin: Nonclinical studies, predominantly in monkey, increased activation of macrophages was noted in a number of organs at $\geq 3$ mg/kg/week, reflective of a systemic inflammatory response. Minimal inflammatory changes (inflammatory cell infiltrate and/or	Subjects with significant cardiac risk factors will be excluded from study participation.

Potential Risk of Clinical Significance	Summary of Data/Rationale for Risk	Mitigation Strategy
response with belantamab mafodotin  Cardiac disorders associated with pembrolizumab	
haemorrhage) were also noted in hearts (atrial epicardium, ventricle endocardium) of single monkeys, which were nonadverse and reversible.
 
Incidence of cardiac events reported to date with belantamab mafodotin was relatively low and mostly grade 1-2.
 
Pembrolizumab: Cardiac disorders including pericarditis, pericardial effusion, and myocarditis, have been reported with pembrolizumab therapy.
	
Close monitoring of vital signs and ECG, troponin, and ECHO will be performed.
 
Treatment as medically indicated. Monitoring of other cardiac parameters as clinically indicated.
 
Dose modifications for myocarditis with pembrolizumab are provided in Table 5.

Hepatotoxicity	
Belantamab mafodotin: In nonclinical studies liver is a target organ for toxicity, with increased liver weights and/or raised hepatobiliary enzymes and transaminases observed in both rat and monkey. These changes in the liver were without clinical consequence in the shorter duration studies and in the rat 13-week study. In the monkey 13-week study, progression of liver toxicity to include minimal multifocal hepatocellular necrosis was observed at all doses administered (<math>\geq 3</math> mg/kg/week).
 
Mild elevations of liver enzymes have been reported in some patients treated with belantamab mafodotin.
 
Pembrolizumab: Hepatitis has been reported with pembrolizumab treatment.
	
Only subjects with well-preserved liver function per the inclusion/exclusion criteria will be allowed on study.
 
Subjects with Hepatitis B (HBV) and C will be excluded.
 
Liver function tests will be frequently monitored. In case of liver abnormalities, management will be implemented according to clinical practice. Subjects that meet liver stopping criteria (Section 5.4.1.1) will be withdrawn from the study.

Nephrotoxicity	
Belantamab mafodotin: Non-clinical safety studies have demonstrated dose dependent and reversible primary glomerular injury and tubular degeneration (in rat and monkey), accompanied by large molecular proteinuria (albuminuria) and enzymuria. Single cell necrosis of the kidney and bladder urothelium was also noted in the 13-week monkey study. Severe tubular degeneration/regeneration and marked glomerulonephritis exacerbated by immune complex disease, likely
	
Subjects will be monitored for kidney function by assessing creatinine, eGFR, electrolytes, and albumin/creatinine ratios (spot urine).
 
Subjects will be educated about the need of maintaining adequate urinary output.

Potential Risk of Clinical Significance	Summary of Data/Rationale for Risk	Mitigation Strategy
	
associated with ADA, led to the early euthanasia of one monkey following 5 weekly doses of 10 mg/kg.
 
Increased albumin/creatinine ratio (albuminuria) not indicative of disease progression has been reported in clinical trials and named patient programs with belantamab mafodotin.
 
Pembrolizumab: Renal disorders, including nephritis and acute kidney injury, have been reported with pembrolizumab treatment.
	
Management will be implemented according to clinical practice.
 
Dose reductions and treatment stopping criteria will be applied according to Section 6.5.
 
Dose modifications for nephritis and renal dysfunction with pembrolizumab are provided in Table 5.

Pulmonary toxicity (pneumonitis)	
Belantamab mafodotin: Nonclinical safety experiments have demonstrated the presence of progressive microscopic changes in the lungs (prominent alveolar macrophages associated with eosinophilic material; mixed perivascular/neutrophilic inflammation) in rats at all doses tested.
 
Cases of pneumonitis, including fatal events, have been observed with belantamab mafodotin although a causal association has not been established.
 
Pembrolizumab: Pneumonitis has been reported with pembrolizumab treatment.
	
Monitoring for clinical signs and symptoms potentially related to pulmonary toxicity. If a participant experiences new or worsening pulmonary symptoms, (e.g., cough, dyspnea) without obvious etiology, appropriate diagnostic evaluation should be performed (see protocol section 6.5.1) and further treatment with belantamab mafodotin delayed (refer to protocol section 6.5.1).
 
An overall benefit/risk assessment should be considered for the participant prior to continuing belantamab mafodotin treatment.
 
Dose modifications for pembrolizumab are provided in Table 5.

Potential Risk of Clinical Significance	Summary of Data/Rationale for Risk	Mitigation Strategy
Potential for Other Laboratory abnormalities	
Belantamab mafodotin: An increased magnitude of AST relative to ALT consistent with increased skeletal troponin I was observed in the single dose monkey study. Increased skeletal troponin I and/or creatine kinase and aldolase was observed in the rat 3-week study.
 
Cases of elevated aspartate aminotransferase (AST), lactic dehydrogenase (LDH) and creatine kinase (CK) alone or concomitant with no clear clinical correlate have been observed in clinical studies.
 
Pembrolizumab: AST and ALT increase have been reported with pembrolizumab treatment.
	
Laboratory parameters will be monitored as outlined in Section 7.
 
Subjects with significant laboratory elevations (<math>\geq 3</math> ULN) should, where possible, have a sample sent to central testing of CK and LDH isoenzyme levels.
 
Dose modifications for pembrolizumab ALT and AST elevations are provided in Table 5.

Embryo-Fetal Toxicity	
Belantamab mafodotin: Nonclinical reproductive studies with belantamab mafodotin have not been conducted. Embryo-fetal toxicity is expected due to the cytotoxic component, cys-mcMMAF via nonspecific uptake and/or BCMA-mediated toxicity (due to reports of BCMA expression in human placental cells [Langat, 2008]).
 
Use of belantamab mafodotin in pregnant women may cause fetal harm.
 
Pembrolizumab: Animal reproduction studies have not been conducted with pembrolizumab; however, in murine models of pregnancy blockade of PD-L1 signaling has been shown to disrupt tolerance to the foetus and to result in an increased fetal loss. These results indicate a potential risk, based on its mechanism of action, that administration of pembrolizumab during pregnancy could cause fetal harm, including increased rates of abortion or stillbirth.
	See Contraception requirements in Section 6.11.1.
Risks Related to Belantamab mafodotin not listed under potential overlapping toxicities		
Immunosuppression	In non-clinical studies belantamab mafodotin has been associated with decrease in immunoglobulins in monkeys at all doses. An increase in	Subjects who have active infection will be excluded.

Potential Risk of Clinical Significance	Summary of Data/Rationale for Risk	Mitigation Strategy
	
immunoglobulins was seen in rats (rats are not an antigen specific species for belantamab mafodotin).
 
MM subjects frequently are immunodeficient due to the underlying condition. Assessment of changes in immunoglobulin levels is challenging in patients with MM.
	Subjects will be monitored for infections and those who develop infection will receive immediate treatment according to standard practice.
Impaired Male and Female Fertility	
In animal studies, belantamab mafodotin treatment has resulted in testicular toxicity and adverse effects on spermatogenesis. Reversibility of testicular and ovarian toxicity is unknown at this time.
 
Ovarian toxicity (luteinized non-ovulatory follicles) was observed in a 3-week rat study (weekly dosing) and was not observed following 12 weeks off dose. In a 13-week rat study where drug was administered once every 3 weeks, these changes were not observed.
	
Men who may wish to father children in the future will be advised to have sperm samples frozen and stored before treatment.
 
Women of child bearing potential who may desire offspring in the future will be counselled about the option of having eggs frozen before treatment.
 
See Contraception requirements in Section 6.11.1

Study Procedures		
Bone marrow aspiration/biopsy	Pain, infection, bleeding may occur after the procedure	Subjects will be treated according to institution's practice
Incidental findings during imaging data acquisition	During the acquisition of imaging data (e.g., MRI, CT, PET, ECHO), non-MM disease or drug related clinical abnormalities could be found by the radiographer or echocardiographer performing the exams.	Copies of all medical images that include non-disease, and clinically relevant abnormalities will be shared with the site for storage.

#### **4.6.2. Benefit Assessment**

Currently there is no cure for MM, and after exhausting available treatment options patients frequently relapse, become refractory, and ultimately die of their disease. This study will test a novel combination of belantamab mafodotin and pembrolizumab to assess safety, tolerability and clinical activity of this treatment. Belantamab mafodotin has been shown to induce immunogenic cell death phenomenon of MM cells in vitro, which provides a rationale for testing it in combination with pembrolizumab. It is reasonable to hypothesise that such combination will benefit MM patients, who are refractory to currently available treatments.

#### **4.6.3. Overall Benefit: Risk Conclusion**

Although there is limited human experience with belantamab mafodotin, and no clinical experience with the combination of belantamab mafodotin with pembrolizumab, given the currently available safety data and the low likelihood of drug-drug interactions between belantamab mafodotin and pembrolizumab, combination therapy may have an acceptable safety profile. Additionally, the combination may provide anti-tumor effect in subjects with MM; but this is unknown.

Of note, excess deaths were noted with pembrolizumab in combination with lenalidomide and dexamethasone (Keynote-185) or in combination with pomalidomide and dexamethasone (Keynote-183) leading the FDA to suspend these phase 3 trials, in addition to other trials of anti-PD[L] therapies in combination with immunomodulatory agents in myeloma or non-Hodgkin's lymphoma were suspended. Please refer to Section 2.3.3 for additional information. This statement does not apply to patients taking KEYTRUDA (pembrolizumab) for an approved indication. The safety and efficacy of using KEYTRUDA (pembrolizumab) for approved, on-label uses have been proven. ([www.fda.gov/Drugs/DrugSafety/ucm574305.htm](http://www.fda.gov/Drugs/DrugSafety/ucm574305.htm)). Considering the measures taken and described in Section 7, to minimize risk to subjects, the potential risks associated with belantamab mafodotin in combination with pembrolizumab noted in Section 4.6.1 are justified by the anticipated benefits that may be afforded to subjects with MM.

## 5. SELECTION OF STUDY POPULATION AND WITHDRAWAL CRITERIA

Specific information regarding warnings, precautions, contraindications, adverse events, and other pertinent information on belantamab mafodotin that may impact subject eligibility is provided in the Investigator's Brochure [[GlaxoSmithKline Document Number 2013N175128\\_09, 2021](#)].

Specific information regarding warnings, precautions, contraindications, adverse events, and other pertinent information on pembrolizumab that may impact subject eligibility is provided in the pembrolizumab approved labelling. For detailed background information on pembrolizumab refer to [[Keytruda SmPC, 2017](#) and [KEYTRUDA PI, 2018](#)].

Deviations from inclusion and exclusion criteria are not allowed because they can potentially jeopardize the scientific integrity of the study, regulatory acceptability or subject safety. Therefore, adherence to the criteria as specified in the protocol is essential.

### 5.1. Inclusion Criteria

Subjects eligible for enrolment in the study must meet all of the following criteria:

1. Provide signed written informed consent, which includes compliance with the requirements and restrictions listed in the consent form
2. Male or female, 18 years or older (at the time consent is obtained)
3. Eastern Cooperative Oncology Group (ECOG) performance status of 0 or 1 ([Appendix 2](#))
4. Subjects must:
  - Has histologically or cytologically confirmed diagnosis of MM, as defined by IMWG, 2014 [[Rajkumar, 2014](#)], and
  - Has undergone stem cell transplant or is considered transplant ineligible, and
  - Has been treated with at least 3 prior lines of prior anti-myeloma treatments including an IMiD (eg. lenalidomide or pomalidomide), a proteasome inhibitor (eg. bortezomib, ixazomib or carfilzomib) and an anti-CD38 antibody alone or in combination. Line of therapy are defined by consensus panel of the International Myeloma Workshop [[Rajkumar, 2011](#)].
  - Has measurable disease defined as one the following:
    - a) Serum M-protein  $\geq 0.5$  g/dL ( $\geq 5$  g/L)
    - b) Urine M-protein  $\geq 200$  mg/24h
    - c) Serum FLC assay: Involved FLC level  $\geq 10$  mg/dL ( $\geq 100$  mg/L) and an abnormal serum free light chain ratio ( $<0.26$  or  $>1.65$ )
5. Subjects with a history of autologous stem cell transplant are eligible for study participation provided the following eligibility criteria are met:
  - a) transplant was  $> 100$  days prior to study enrolment
  - b) no active infection (s)
  - c) subject meets the remainder of the eligibility criteria outlined in this protocol
6. Adequate organ system functions as defined in [Table 3](#)

**Table 3 Adequate Organ System Function**

System	Laboratory Values
Hematologic	
Absolute neutrophil count (ANC) 	$\geq 1.0 \times 10^9/L$
Hemoglobin	$\geq 8.0 \text{ g/dL}$
Platelets	$\geq 75 \times 10^9/L$
Hepatic	
Total bilirubin	$\leq 1.5 \times \text{ULN}$ (Isolated bilirubin $> 1.5 \times \text{ULN}$ is acceptable if bilirubin is fractionated and direct bilirubin $< 35\%$ )
AST and ALT	$\leq 2.5 \times \text{ULN}$
Renal	
eGFR 	$\geq 40 \text{ mL/min}$
Spot urine (albumin creatinine ratios)	$< 500 \text{ mg/g (56 mg/mmol)}$
Cardiac	
LVEF (Echo)	$\geq 50\%$
QTcF interval 	$< 470 \text{ msec}$

- Without any Growth factor support (e.g. colony stimulating factors (including granulocyte colony stimulating factor [G-CSF], granulocyte-macrophage colony-stimulating factor [GM-CSF], recombinant erythropoietin) or any thrombopoietin receptor agonists) within 2 weeks before the first dose of study drug.
- As calculated by Modified Diet in Renal Disease (MDRD) formula
- The QT interval should be corrected for heart rate by Fridericia's formula (QTcF)

**NOTE:** Laboratory results obtained during Screening should be used to determine eligibility criteria. In situations where laboratory results are outside the permitted range, the investigator may retest the subject and the subsequent within range screening result may be used to confirm eligibility. If laboratory results were obtained more than 72 hours before first dose, laboratory results must be redone within 72 hours prior to first dose to confirm eligibility.

- All prior treatment-related toxicities (defined by National Cancer Institute-Common Toxicity Criteria for Adverse Events (NCI-CTCAE), version 4.03, 2010) [NCI, 2010] must be  $\leq$  Grade 1 at the time of enrollment except for alopecia and Grade 2 neuropathy.
- A female subject is eligible to participate if she is not pregnant or breastfeeding, and at least one of the following conditions applies:
  - Is not a woman of childbearing potential (WOCBP)
  - OR
  - Is a WOCBP and using a contraceptive method that is highly effective (with a failure rate of  $< 1\%$  per year), preferably with low user dependency, as described in [Appendix 8](#) during the intervention period and for at least 9 months after the last dose of study intervention and agrees not to donate eggs (ova, oocytes) for the purpose of reproduction during this period. The investigator should evaluate the effectiveness of the contraceptive method in relationship to the first dose of study intervention. Contraceptive use by

women should be consistent with local regulations regarding the methods of contraception for those participating in clinical studies.

A WOCBP must have a negative highly sensitive serum pregnancy test (as required by local regulations) within 72 hours of dosing on C1D1 and agree to use effective contraception during the study and for 4 months after the last dose of study medication.

Additional requirements for pregnancy testing during and after study intervention are located in [Appendix 8](#).

The investigator is responsible for review of medical history, menstrual history, and recent sexual activity to decrease the risk for inclusion of a woman with an early undetected pregnancy.

9. Male subjects:

- Male subjects are eligible to participate if they agree to the following from the time of first dose of study until 6 months after the last dose of study treatment to allow for clearance of any altered sperm:

- Refrain from donating sperm

PLUS either:

- Be abstinent from heterosexual intercourse as their preferred and usual lifestyle (abstinent on a long term and persistent basis) and agree to remain abstinent

OR

- Must agree to use contraception/barrier as detailed below:

- Agree to use a male condom, even if they have undergone a successful vasectomy, and female partner to use an additional highly effective contraceptive method with a failure rate of <1% per year as described in [Appendix 8](#) when having sexual intercourse with a woman of childbearing potential who is not currently pregnant

- Contraceptive use by men should be consistent with local regulations regarding the methods of contraception for those participating in clinical studies

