
 
Without any Growth factor support (e.g. colony stimulating factors (including granulocyte colony stimulating factor [G-CSF], granulocyte-macrophage colony-stimulating factor [GM-CSF], recombinant erythropoietin) or any thrombopoietin receptor agonists) within 2 weeks before the first dose of study drug.
 
As calculated by Modified Diet in Renal Disease (MDRD) formula
 
The QT interval should be corrected for heart rate by Fridericia's formula (QTcF)
 
	

- All prior treatment-related toxicities (defined by National Cancer Institute-Common Toxicity Criteria for Adverse Events (NCI-CTCAE), version 4.03, 2010) [NCI, 2010] must be  $\leq$  Grade 1 at the time of enrollment except for alopecia, and Grade 2 neuropathy.
- A female subject is eligible to participate if she is not pregnant or breastfeeding, and at least one of the following conditions applies:
  - Is not a woman of childbearing potential (WOCBP)  
OR
  - Is a WOCBP and using a contraceptive method that is highly effective (with a failure rate of  $< 1\%$  per year), preferably with low user dependency, as described in [Appendix 8](#) during the intervention period and for 4 months after the last dose of study intervention and agrees not to donate eggs (ova, oocytes) for the purpose of reproduction during this period. The investigator should evaluate the effectiveness of the contraceptive method in relationship to the first dose of study intervention. Contraceptive use by women should be consistent with local regulations regarding the methods of contraception for those participating in clinical studies.

A WOCBP must have a negative highly sensitive serum pregnancy test (as required by local regulations) within 72 hours of dosing on C1D1 and agree to use effective contraception during the study and for 4 months after the last dose of study medication.

Additional requirements for pregnancy testing during and after study intervention are located in [Appendix 8](#).

The investigator is responsible for review of medical history, menstrual history, and recent sexual activity to decrease the risk for inclusion of a woman with an early undetected pregnancy.

- Male Subjects:

- Male subjects are eligible to participate if they agree to the following from the time of first dose of study until 6 months after the last dose of study treatment to allow for clearance of any altered sperm :

- Refrain from donating sperm

PLUS either:

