#### 6.11.1.1. Female Subjects

In order to participate in the study, WOCBP must adhere to the contraception requirement (from the day of study medication initiation) during the study and for 9 months after the last dose of study treatment. If there is any question that a WOCBP will not reliably comply with the requirements for contraception, that subject should not be entered into the study. Full details are in [Appendix 8](#).

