#### 6.11.1.2. Male Subjects

Male subjects with female partners of child bearing potential must comply with the contraception requirements highlighted in Section [5.1](#) from the time of first dose of study medication until 140 days after the last dose of belantamab mafodotin. Details on contraceptive options for subjects with a partner of childbearing potential are in [Appendix 8](#).

Men with a pregnant or breastfeeding partner must agree to remain abstinent from penile-vaginal intercourse or use a male condom during each episode of penile penetration from the time of first dose of study until 6 months after the last dose of study treatment to allow for clearance of any altered sperm.

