### 7.3.2. **Pregnancy**

Do not collect pregnancy information for female subjects known to be pregnant during the screening phase or before exposure to study.

The need for a screening pregnancy test depends on whether a female subject is of childbearing potential or non-childbearing potential.

If a female subject is of childbearing potential, she must have a serum  $\beta$ -human chorionic gonadotropin ( $\beta$ -HCG) pregnancy test performed within 72 hours prior to the first dose of study treatment. Subjects with positive pregnancy test result must be excluded from the study. Subjects with negative pregnancy test result must agree to use an effective contraception method as described below during the study and for 4 months following the last dose of study treatment.

Details of all pregnancies in female subjects will be collected after the start of study treatment and for 4 months following last dose of belantamab mafodotin.

Details of all pregnancies for female partners of male subjects will be collected after the start of study treatment and 6 months following last dose of belantamab mafodotin.

If a pregnancy is reported, the investigator must inform GSK within 24 hours of learning of the pregnancy and must follow the procedures outlined in [Appendix 8](#).

Abnormal pregnancy outcomes (e.g., spontaneous abortion, fetal death, stillbirth, congenital anomalies, ectopic pregnancy) are considered SAE.

Pregnancy testing (urine or serum as required by local regulations) should be conducted at the end of relevant systemic exposure (4 months after the last dose of belantamab mafodotin) and correspond with the time frame for female subject contraception in Section [5.1](#).

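### Post-treatment contraception periods conflict (women 9 versus 4 months, men 6 months versus 140 days), and Section 7.3.2 and Table 10 disagree on the 4-month pregnancy check

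*Protocol*

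**What the plan says.** **Women of childbearing potential.** Criterion 8 in Section 5.1 of the Protocol requires a highly effective method "during the intervention period and for at least 9 months after the last dose of study intervention". The next paragraph of the same criterion has her "agree to use effective contraception during the study and for 4 months after the last dose of study medication". Section 6.11.1.1 applies the requirement "during the study and for 9 months after the last dose of study treatment". The synopsis (Key Inclusion Criteria) repeats the highly effective sentence of Section 5.1, but there it reads "during the intervention period and for 4 months after the last dose of study intervention". Section 7.3.2 asks for an effective method "as described below during the study and for 4 months following the last dose of study treatment".

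**Men.** Criterion 9 in Section 5.1 runs "until 6 months after the last dose of study treatment to allow for clearance of any altered sperm", and the synopsis agrees. Section 6.11.1.2 says that men with partners of childbearing potential "must comply with the contraception requirements highlighted in Section" 5.1, and then ends the period 140 days after the last belantamab mafodotin dose. Its second paragraph, on men whose partner is pregnant or breastfeeding, returns to 6 months.

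**Pregnancy check.** Section 7.3.2 calls for a urine or serum test 4 months after the last belantamab mafodotin dose and ties it to the female contraception period in Section 5.1. Table 10 marks the pregnancy-test row in both the PFS and OS follow-up columns. Note 9, which those marks carry, makes the end-of-treatment (EOT) test the final one and asks only for a telephone assessment at 4 months.

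**Appendix 8.** Criterion 8 states: "Additional requirements for pregnancy testing during and after study intervention are located in" Appendix 8. Section 6.11.1.1 also sends the reader there for the full details.

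**The concern.** Table 2 warns of fetal harm from belantamab mafodotin, and its only listed mitigation for embryo-fetal toxicity is the contraception requirement in Section 6.11.1. That section contradicts Section 5.1 for men, and the synopsis and Section 7.3.2 for women. The female conflict also sits within a single inclusion criterion, and Section 5 allows no deviations from the criteria. A site must therefore apply a rule that reads two ways. If it works from the synopsis, Section 7.3.2 or the second statement in criterion 8, it would tell a woman 4 months; from Section 6.11.1.2 it would tell a man 140 days.

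If 9 months is the intended period for women, the surveillance does not match it. The call and the formal pregnancy collection window both stop at 4 months, and so does the test in Section 7.3.2. A site also cannot tell from the text whether a test is due at 4 months at all.

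**Working it through.** The Protocol derives no figure here, so the check sets the statements side by side and converts them to days, taking 1 month = 365.25 / 12 = 30.44 days.

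| Item | Longer or stricter statement | Shorter or lighter statement |
|---|---|---|
| Women, contraception | at least 9 months (5.1 criterion 8, first statement); 9 months (6.11.1.1) | 4 months (5.1 criterion 8, second statement; synopsis; 7.3.2) |
| Men, contraception | 6 months (5.1 criterion 9; synopsis; 6.11.1.2 second paragraph) | 140 days (6.11.1.2 first paragraph) |
| Check at 4 months | urine or serum test (7.3.2; Table 10 row marks) | telephone call, EOT test is final (Table 10 note 9) |

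**Women.** 9 × 30.44 = 273.9 days and 4 × 30.44 = 121.8 days. The difference is 152.2 days.

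**Men.** 6 × 30.44 = 182.6 days, and 182.6 − 140 = 42.6 days. The anchors differ: 6 months runs from the last study treatment, 140 days from the last belantamab mafodotin dose. The two drugs are normally given on the same day. Section 4.2.1 lets pembrolizumab slip by up to 3 days within a cycle, which gives at most 42.6 + 3 = 45.6 days. The anchor does not explain the gap.

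**Last test.** Section 4.2.2 places EOT at 30 ± 7 days after the last dose, so 23 to 37 days. From there to 4 months is 121.8 − 37 = 84.8 to 121.8 − 23 = 98.8 days. It is longer if new therapy brings EOT forward.

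**Months 4 to 9 in women.** Formal collection of pregnancies in female subjects ends at 4 months in both Section 7.3.2 and Appendix 8. General follow-up continues under Table 10 notes 3 and 4. Over 152.2 days that is 152.2 / 21 = 7.2 PFS visits or 152.2 / 84 = 1.8 OS contacts for a woman still in follow-up. None has a pregnancy-specific content for that period.

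**Can the text be reconciled?** One reading is two tiers: a highly effective method for 9 months and an effective one for 4. The synopsis rules that out, because it attaches 4 months to the highly effective sentence that carries 9 months in Section 5.1. Section 7.3.2 does not help either: it ties its 4-month test to the Section 5.1 period, which reads both ways. Appendix 8 lists acceptable methods and the pregnancy collection windows (4 months for female subjects, 6 months for partners of male subjects), but no contraception duration and no test schedule.

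**The case against.** The best defence is that Section 5.1 can be obeyed as written. All criteria must be met, and 9 months of highly effective contraception also satisfies 4 months of effective contraception. For men, 140 days is a lone figure: Section 5.1, the synopsis, the second paragraph of Section 6.11.1.2 and both partner collection windows all use 6 months. This stands. It shows which figure governs on a literal reading and that 140 days looks like a leftover. It does not stop a site from following the operative sections that give the shorter period.

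The 4-month figure is also not arbitrary. Section 7.3.2 ties it to the end of systemic exposure, and with the half-life of 12 to 14 days in Section 2.2.5.1, 121.8 days is about 9 to 10 half-lives. That stands too, so the choice between 9 and 4 months belongs to the sponsor. It does not remove the need to choose.

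Two stronger readings are tempting but unsupported.

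- A reader might infer that a pregnancy in months 4 to 9 would be missed. Section 7.3.2 makes abnormal pregnancy outcomes SAEs and requires a reported pregnancy to be notified within 24 hours. Section 7.3.1.1 and Table 10 note 5 collect related SAEs through follow-up. Appendix 8 covers related SAEs from a post-study pregnancy, although the investigator need not seek them. What could go formally uncollected is mainly a pregnancy without an adverse outcome, or one with an outcome judged unrelated.
- A reader might infer that the 70-day pregnancy reporting window in Sections 5.5.2, 6.13 and 7.3.1.1 contradicts the 4- and 6-month collection windows. Those sections set 70 days specifically for participants who stay on belantamab mafodotin after the final data cut-off. It is a special rule for a named group, and whether it is too short is a sponsor choice.

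**Conclusion.** The contraception text is wrong as written and should be corrected. A site following the shorter statements would instruct a period about 152 days shorter for women, or about 43 days shorter for men, than Section 5.1 requires on its literal reading. Whether a test or a call is due at 4 months is unresolved.

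The day counts assume 30.44 days per month and, for men, the same last-dose date for both drugs. How many participants are affected is unknown: the Protocol does not say how many women of childbearing potential it expects among up to 40 evaluable subjects. The consent form was not available, so what participants were actually told cannot be judged. Adverse pregnancy outcomes judged related would still be captured as SAEs. ORR, the sample size and the error rates are untouched.

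**What to change.** State one duration per sex in the synopsis and in Sections 5.1, 6.11.1.1, 6.11.1.2 and 7.3.2:

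- Men: 6 months. Delete the 140-day figure from Section 6.11.1.2.
- Women: the 9 months of Sections 5.1 and 6.11.1.1, unless the sponsor documents that the exposure-based 4 months is what was intended. Remove the other figure wherever it occurs, including the second statement in criterion 8.

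Make Section 7.3.2 and Table 10 note 9 agree on a test or a call. Align that check and the female pregnancy collection window (Section 7.3.2 and Appendix 8) with the chosen contraception period. Put the durations and the check schedule in Appendix 8 as well, since Sections 5.1 and 6.11.1.1 point there. The 6-month partner collection window can stay.

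The cost is wording, a consent-form check and a site letter. If 9 months is kept, the pregnancy check for each woman of childbearing potential falls later, or one is added, and pregnancy collection in women runs longer.
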